6.2 Missing Data

6.2.1 Missing Baseline Data

Missing baseline values will not be imputed and summaries will be based on all available

data.

6.2.2 Missing Primary Outcome Data

The plan for handling missing primary outcome data is outlined in section 6.5.1.3 below.

6.2.3 Missing Secondary Outcomes Data

In general, missing outcome values for secondary endpoints will not be imputed and analyses will be based on all available data. Multiple imputation may be used for specific analyses (e.g., cost analysis).

6.3 Crossover

Crossovers (patients who after randomization switch from the allocated treatment to the non-allocated treatment) are expected to be few in this trial. Patients randomized to TV annuloplasty who do not receive it during the trial can be considered crossovers. In addition, patients who are randomized to no annuloplasty but receive it during the index procedure are considered to have crossed over. As the primary analysis is by intention to treat, crossovers will be analyzed as belonging to the group to which they were randomized. Given the short duration between randomization and surgery, crossovers are assumed to be rare (no more than 3%).

6.4 Patient Characteristics

6.4.1 Patient Disposition

Disposition will be summarized in the screened and ITT populations.

Disposition summaries of the screened population will include:

- The number of patients screened
- The number and percentage of screened patients eligible
- The number and percentage of screened patients ineligible and the reasons for ineligibility summarized as the number and percentage of ineligible patients who met each ineligibility criteria
- The number and percentage of eligible patients randomized

Disposition in the ITT population will be summarized by randomization group and will include:

- The number of patients randomized
- The number and percentage of patients who received their assigned procedure
- The number and percentage of patients withdrawn or lost to follow-up by the primary outcome visit at 24 months and the primary reason for withdrawals
- The number and percentage of patients withdrawn or lost to follow-up by the final study visit at 60 months and the primary reason for withdrawals

6.4.2 Protocol Deviations

Protocol deviations and violations are defined as deviations from the procedures outlined in the protocol. There is no “Per Protocol” population defined for this study. All statistical analyses and summaries will be conducted on an intent-to-treat basis.

6.4.3 Patient Characteristics

6.4.3.1 Demographic characteristics

Demographics including age, gender, race and ethnicity will be summarized by randomization assignment using the appropriate descriptive statistics.

6.4.3.2 Baseline characteristics

Baseline characteristics will be summarized by randomization assignment using the appropriate descriptive statistics. The specific baseline variables collected are detailed in the protocol and include medical history, physical exam findings, medications, laboratory assessments, echocardiographic measures, quality of life, and functional status.

6.4.3.3 Operative characteristics

Operative data including primary procedure type, duration of operation, duration of aortic cross clamp time, duration of cardiopulmonary bypass time, and concomitant procedures will be summarized by randomization assignment using the appropriate descriptive statistics.

6.5 Primary and Secondary Outcome Analyses

All analyses will be performed using the ITT population.

6.5.1 Analysis of the Primary Outcome and Determination of Sample Size

The primary outcome is treatment failure defined as the composite of (1) death from any cause, (2) reoperation for TR, (3) presence of severe TR at two years post randomization or, for patients enrolled with less than moderate TR and annular dilatation, progression by two grades (i.e., from none/trace TR to moderate TR) at two years. The null hypothesis is that there is no difference in the probability of treatment failures at two years post randomization between patients randomized to undergo TV repair during MVS compared to patients randomized to undergo MVS alone. The primary null hypothesis will be tested in an intent-to-treat analysis using a 0.05 level two-tailed normal approximation (Wald) test.

6.5.1.1 Determination of Sample Size

Based on previously published data we assume that at two years post randomization, 25% of patients treated with only MVS will experience the primary composite endpoint (Goldstone et al., 2014; Koelling, Aaronson, Cody, Bach, & Armstrong, 2002; Nath, Foster, & Heidenreich, 2004). We believe a meaningful effect worth detecting is at least a 50% relative reduction to 12%, for patients undergoing TV annuloplasty in addition to MVS. A total of 400 patients, randomized with equal probability to each arm, provides approximately 90% power to detect such a

difference. For simplicity, power is based on a 0.05 level two-tailed chi-square test. The sample size takes account of a potential single interim analysis to be performed in addition to the final analysis, and a minimal (less than 3%) rate of crossover.

6.5.1.2 Primary Analysis

A log binomial regression model will be used to estimate and test differences in treatment failure between randomization groups. Similar to the logistic regression model, the log-binomial model is a generalized linear model. The models differ only in the link function used for the "success" probability p ; logit (log odds) for logistic regression and log (log p) for log-binomial. The different links parameterize the model differently, with parameters of the log-binomial model yielding log relative risks rather than the log odds ratios of the logistic model.

The basic form of the log binomial models is:

$$\log P[Y_i = 1|X_{1i}, X_{2i}] = \beta_0 + \beta_1 X_{1i} + \beta_2 X_{2i},$$

where Y_i is a binary indicator of treatment failure for the i^{th} patient, X_{1i} is a binary indicator of randomization assignment for the i^{th} patient and X_{2i} is an indicator of moderate or less TR at baseline, a factor by which randomization will be stratified. While randomization will also be stratified by randomizing center, the analysis will not adjust for center due to their relatively large number compared to the proposed sample size. The exponentiated estimate of β_1 ($e^{\hat{\beta}_1}$) in this model is the risk ratio for the composite endpoint for patients randomized to TV repair compared to patients randomized to no TV repair. The risk ratio and its associated 95% confidence interval will be used to quantify the relative risk of the composite endpoint. Differences between randomization groups in the risk of the composite endpoint will be determined by testing the null hypothesis $H_0: \beta_1 = 0$ versus a two-sided alternative ($H_1: \beta_1 \neq 0$) using a 0.05 level intention-to-treat normal approximation test (i.e., the Wald test).

6.5.1.3 Imputation of Missing Primary Endpoint Data

We expect relatively few patients to be missing the primary endpoint due to withdrawal or refusal. Patients with missing data will have their 24 month status imputed via multiple imputation assuming that the data are missing at random. The imputation model will be stratified by randomization assignment and include age, sex, randomization strata for moderate or less TR at baseline, degree of TR at 6 months, and degree of TR at 12 months. Since this model includes a mixture of variables types (i.e. continuous, ordinal, and binary), a fully conditional specification method will be used (Berglund, Heeringa, & SAS Institute., 2014).

The main feature of the imputation approach is the creation of a set of clinically reasonable imputations for treatment failure for each patient with missing data. This will be accomplished using a set of repeated imputations created by predictive

models based on the majority of participants with complete data. The imputation models will reflect uncertainty in the modeling process and inherent variability in patient outcomes, as reflected in the complete data. Thirty datasets will be imputed.

After the imputations are completed, all of the data (complete and imputed) will be combined and the analysis performed for each imputed-and-completed dataset. Rubin's method of multiple (i.e., repeated) imputation will be used to estimate treatment effect (Rubin & Schenker, 1986).

6.5.1.4 Assessment of Balance of the Randomization

The success of the randomization procedure in balancing important covariates between randomization groups will be assessed. Continuous measures will be compared using t-tests, while chi-square tests will be used to compare categorical variables. As 400 patients will be randomized, no substantial imbalances are expected. However, should any covariate differ significantly between treatment groups at the 0.01 level, and be substantively large, we will adjust for those covariates in a secondary analysis of the primary endpoint.

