We propose considering increasing sample size should the observed primary endpoint event rate among patients randomized to no repair of the TV be appreciably less than the assumed rate of 25%. The planned sample size of 400 patients has been determined to ensure that power is at least 90% to detect a 52% relative reduction of “failure” for patients randomized to tricuspid repair compared to no repair. Should the “failure” rate among controls be 20%, 400 patients provides approximately 83% power to detect a 52% relative reduction; for a 15% “failure” rate among controls there is approximately 70% power to detect a 52% relative reduction. Therefore, we suggest that the primary endpoint event rate be examined in control patients, using the same analysis set to be used for the interim analysis, and that the sample size be increased by up to 100 additional patients in order to maintain 80% power under the original alternative hypothesis for control rates as low as 15%. If no interim analysis is conducted or accrual is complete at the time of the first interim analysis, the sample size re-estimation will not be considered.

Assessment of Balance of the Randomization

The success of the randomization procedure in balancing important covariates between randomization groups will be assessed at the interim analysis and at the final analysis. Continuous measures will be compared using t-tests, while chi-squared tests will be used to compare categorical variables. As 400 patients will be randomized, no substantial imbalances are expected. However, should any covariate differ significantly between treatment groups at the 0.01 level, and be substantively large, we will adjust for those covariates in a secondary analysis of the primary endpoint.

Additional analysis of the primary endpoint

A subgroup analysis of the primary endpoint will be performed with subgroups defined by whether or not patients received a CABG procedure during the initial surgery. This analysis will be performed in the same manner as that described for the primary analysis.

Analyses of Secondary Endpoints

Individual components of the primary endpoint

Mortality: Differences in the rate of mortality between randomization groups over the first 24 months and the planned 60 months of follow-up will be assessed using Cox proportional hazards regression.

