3.1.2 Randomization and Masking

Patients will be randomly assigned (1:1) to MVS + TV annuloplasty or MVS alone. Patient randomization will be stratified by TR severity and by clinical center. The randomization procedure will be performed intra-operatively, following the placement of the TEE probe and after visualization and confirmation of cardiac anatomy eligibility, in order to minimize the likelihood of enrolling patients in the study with unexpected surgical contra-indications to TV repair. Randomization will be performed centrally through a Web-based data collection system that automates the delivery of the randomization assignments. The treatment assignment will be viewed by the site coordinator electronically, in a secure fashion, and electronic verification of the treatment assignment will be required before proceeding with the treatment intervention.

Neither patients nor investigators will be blinded to treatment assignment due to the nature of the treatment intervention. Investigators will, however, be blinded to all data from other clinical sites, except serious unexpected AEs that are possibly or probably related to the investigational procedure for IRB/REB/EC reporting purposes. All echocardiograms will be analyzed by echocardiography core laboratory (Echo Core Lab) personnel who will be blinded to clinical outcomes. Adverse events (AEs) will be adjudicated by an Event Adjudication Committee (EAC) and trial oversight will be provided by an independent Data and Safety Monitoring Board (DSMB).

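### The secondary adjusted analysis of the primary endpoint picks its covariates by baseline significance tests at 0.01 plus an undefined size condition, so it does not favour prognostic factors; the primary analysis is unaffected

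*SAP*

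**What the plan says.** SAP 6.5.1.4 opens: "The success of the randomization procedure in balancing important covariates between randomization groups will be assessed". The method is: "Continuous measures will be compared using t-tests, while chi-square tests will be used to compare categorical variables". The consequence has two conditions. The first is statistical: the rule applies "should any covariate differ significantly between treatment groups at the 0.01 level". The second concerns the size of the difference and also fixes the status of the analysis: the imbalance must hold up "and be substantively large, we will adjust for those covariates in a secondary analysis of the primary endpoint". Significance is thus necessary but not sufficient.

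The protocol (Analytical Plan, Assessment of Balance of the Randomization) has the same rule and adds that balance "will be assessed at the interim analysis and at the final analysis".

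Neither document lists the covariates to be tested or puts a number on the size condition. The nearest thing to a candidate list is SAP 6.4.3.2, which names open-ended groups: "medical history, physical exam findings, medications, laboratory assessments, echocardiographic measures, quality of life, and functional status".

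The primary model in SAP 6.5.1.2 is fixed in advance. It contains treatment and one further term, which "is an indicator of moderate or less TR at baseline, a factor by which randomization will be stratified".

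**The concern.** When randomization has worked, every baseline difference between arms is due to chance. A p-value for that difference says nothing about whether the covariate predicts treatment failure, and prognostic value is what makes adjustment useful. Under this rule an irrelevant covariate with p = 0.005 can enter the model, while a strongly prognostic one with p = 0.02 stays out.

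The size condition does not repair this. It concerns how large the imbalance is, not how prognostic the covariate is. With no threshold stated, it is a judgement made with data by arm in view.

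At stake is the usefulness of one secondary analysis: whether it is run at all, what it contains, and whether it gains the precision that known prognostic factors could give.

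**Working it through.** **1. The plan's own figure.** Inputs from SAP 6.5.1.1: 25% versus 12%, 200 per arm, two-sided 0.05.

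- Pooled rate 0.185. SE under the null = √(2 × 0.185 × 0.815 / 200) = 0.03883.
- SE under the alternative = √((0.25 × 0.75 + 0.12 × 0.88) / 200) = 0.03828.
- Power = Φ((0.13 − 1.96 × 0.03883) / 0.03828) = Φ(1.41) = 92.0%.
- With the final critical value of 1.969 (SAP 6.6): 91.9%. Adding 1.5% crossover in each arm: 90.2%. With 3% crossover in the repair arm only: 90.0%.

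The stated 90% or so is reproduced once the SAP's own allowances are applied. Expected failures are 200 × 0.25 + 200 × 0.12 = 74.

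**2. How often the significance condition is met.** For k independent covariates under valid randomization, P(at least one p < 0.01) = 1 − 0.99^k. The value of k is an assumption.

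| k | 5 | 10 | 15 | 20 | 30 | 40 |
|---|---|---|---|---|---|---|
| P(at least one) | 4.9% | 9.6% | 14.0% | 18.2% | 26.0% | 33.1% |

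These are upper bounds for the actual rule, because the size condition can only remove covariates. Correlation among baseline measures, for example the several right ventricular (RV) measures, would also tend to lower them. So in at least 67% (k = 40) to 95% (k = 5) of trials nothing would be added to the TR stratum.

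**3. What imbalance the test requires.** At 200 per arm, p < 0.01 needs a standardized difference of 2.588 × √(2/200) = 0.26. For a binary factor at 50% prevalence this is 2.576 × √(2 × 0.25/200) = 12.9 percentage points. At 20% prevalence it is 2.576 × √(2 × 0.16/200) = 10.3 points.

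**4. Whether the rule finds prognostic factors, and what it gains.** A simulation used 4,000 trials per setting with n = 400. Its assumptions, none of which the documents supply, were: 20 independent normal covariates, 3 of them prognostic, marginal rates of 25% and 12%, and a logistic Wald test standing in for the log-binomial model. No TR-stratum term was included, and selection used p < 0.01 alone.

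| Log-odds per SD | Power, unadjusted | Power, selected at p < 0.01 | Power, 3 pre-specified |
|---|---|---|---|
| 0.4 | 92.8% | 92.8% | 94.4% |
| 0.6 | 92.0% | 92.1% | 95.1% |
| 0.8 | 92.5% | 92.7% | 96.5% |

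Between 13% and 16% of flagged covariates were prognostic, in line with their share of the candidates (3/20 = 15%). The test therefore did not favour them. Selection gained essentially no power, while pre-specification gained about 2 to 4 points. Type I error was 4.9% to 5.6% for all three approaches (Monte Carlo standard error about 0.3 points).

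**The case against.** The strongest case on the other side is that little depends on this rule. The primary estimate and test are fixed, the TR stratum is always in the model, and the contingent analysis is only secondary. Selection uses baseline values and arm, not outcomes, so the test itself cannot be used to steer the treatment effect. The SAP's Purpose section and 6.1 also permit further exploratory analyses, with unplanned ones labelled as such. All of this stands and is why the point is small. The last argument is only a partial answer, because an analysis added that way is not pre-specified.

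A reader might infer more than the documents support:

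- **That error rates are inflated, or that the primary result becomes data-driven.** The rule does not touch the primary model, and the simulation found type I error near 5% under every approach.
- **That this is the robustness check on the primary result.** The SAP gives it no such role. The analysis it calls a sensitivity analysis of the primary endpoint is the visit-window one in 6.5.1.6, and the protocol looks to MACCE for supporting evidence.
- **That usually no adjusted analysis is run.** The primary analysis always adjusts for the TR stratum. What is usually missing is adjustment beyond it.
- **That covariates are chosen after unblinding.** Neither document says so. The tests do need arm assignment, and the protocol places them at the interim and final analyses. But the trial is open label ("Neither patients nor investigators will be blinded to treatment assignment due to the nature of the treatment intervention"), so the safer statement is that the judgement is made on data viewed by arm.
- **That chance triggering is as common as 18% to 33%.** Those values need 20 to 40 independent tests and ignore the size condition. With 5 to 10 covariates the bound is 4.9% to 9.6%.

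**Conclusion.** The point holds as a cheap improvement to a secondary analysis. The covariate rule responds to chance imbalance without regard to prognosis, and its candidate list and size threshold are left open. At most 5% to 33% of trials would meet the significance condition for any covariate, assuming 5 to 40 independent tests, so further adjustment would usually not take place. The loss is analyst discretion plus roughly 2 to 4 power points, the latter resting on assumed prognostic strengths and a logistic stand-in. The primary conclusion does not depend on it.

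**What to change.** In SAP 6.5.1.4 and the matching protocol section, replace the significance-triggered rule with one adjusted secondary analysis of the primary endpoint that is always run. Use the TR stratum plus a short list of prognostic baseline values already collected, fixed before data lock. Possible entries are age, sex, atrial fibrillation history (the medical history form captures arrhythmias), RV function and LVEF (both measured under Protocol Appendix I). The choice is for the trial team. Age, sex and TR stratum are already named for the imputation model, so agreeing a list is feasible. Present baseline balance descriptively; if a check on the conduct of randomization is wanted, keep it separate from covariate choice.

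The cost is wording in two documents; the SAP allows its own revision until data lock. Four downsides need handling:

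- **Length of the list.** Treatment plus six single-parameter covariates gives 74/7 = 10.6 expected failures per parameter, so the list must stay short and RV function should be coded economically.
- **Imputation.** Covariates added to the outcome model should also enter the imputation model in SAP 6.5.1.3.
- **Missing baseline values.** SAP 6.2.1 does not impute them, so added covariates could drop patients unless a method is stated.
- **Convergence.** A log-binomial model with several covariates may not converge. SAP 6.1 allows another link or technique in general terms; name the fallback here.

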6.5.1.5 Examination of Subgroups

A subgroup analysis of the primary endpoint will be performed with subgroups defined by whether or not patients received a CABG procedure during the initial surgery. This analysis will be performed in the same manner as that described for the primary analysis.

6.5.1.6 Impact of COVID-19 Pandemic

Due to the COVID-19 pandemic, patients randomized after January 2018 may be unable to do the on-site, in-person two-year follow up visit. To mitigate the risk of missing primary endpoint data, a revision to the protocol was issued via a study wide memo to widen the two-year visit window from ± 60 days to ± 120 days. The number and percentage of two-year visits missed due to COVID-19 and the number and percentage done outside of the original ± 60 day window due to COVID-19 will be reported.

The primary analysis will be conducted as outlined in section 6.5.1.2 using all available two-year visit echocardiogram results with missing data imputed as outlined in section 6.5.1.3. A sensitivity analysis excluding data collected outside of the original ± 60 day window due to COVID-19 will be conducted to explore the impact of enlarging the window of capture.

6.5.2 Analyses of Secondary Clinical Endpoints

6.5.2.1 Clinical and Functional Outcomes

MACCE: The rate of major cerebrovascular or cardiac events (defined as the

composite event of death, stroke, and serious heart failure events) will be compared between randomization groups over 24 months post-randomization using a Cox proportional hazards regression model.

Reoperation for TR: The difference in the rate of requiring subsequent TV annuloplasty after the initial MVS will be compared between randomization groups over 24 months post-randomization. Reoperation for TR may not occur because death from any cause precedes the event; thus, it is possible that censoring patients at all-cause mortality will lead to biased estimates when analyzing time to first event. Therefore, competing risks analysis using the methods of Fine and Gray (Fine & Gray, 1999) will be used to estimate group differences.

NYHA: The distribution of NYHA at 30 days, 6, 12 and 24 months will be presented for each randomization arm and compared using chi-squared tests.

Diuretic Use: The distribution of diuretic use at 30 days, 6, 12 and 24 months will be presented for each randomization arm and compared using chi-squared tests.

Six Minute Walk: Differences between groups in the distances travelled during the 6MWT at 30 days, 6, 12 and 24 months will be compared using Wilcoxon Rank-Sum tests.

Gait Speed Tests: Differences between groups in gait speed at 12 and 24 months will be compared using Wilcoxon Rank-Sum tests.

